#### AE Grading for Injection Site Reactions

The protocol contains contradictory information on the severity scale to be used when evaluating Injection Site Reactions (ISRs). The protocol states that ISRs should be evaluated for severity using NCI-CTCAE version 5.0 which is a 5-point scale(grade1-5), however, the table included in the protocol, Table 8, is a 3-point scale(grade1-3), this table was included in error.

The data collection via the eCRF was set-up according to the 5-point scale so the data has been collected as needed, therefore no impact on data collection, analysis, and interpretation as it follows standard reporting.

#### 4.3.8.4 *Clinical Laboratory Tests*

Blood and urines samples for safety analysis of clinical chemistry, including liver enzymes, hematology, hemostasis, and urinalysis parameters will be obtained as specified in the Schedule of Assessments (Table 1 and Table 2 of the protocol) and processed using local laboratory. Albumin, calprotectin, microbiome and blood markers analysis will be processed by central laboratory. For purposes of analysis and reporting, laboratory values will be standardized using the International System of Units (SI).

Clinical Laboratory evaluation results will be compared to laboratory reference ranges, with those values outside of the applicable range flagged as high or low. All local laboratory reports will be reviewed by the Investigator and parameters out of normal range assessed as “clinically significant” or “not clinically significant”.

All available clinical laboratory evaluations will be summarized descriptively by apraglutide dose levels and in total using descriptive statistics (n, arithmetic mean, median, minimum, and maximum) for hematology and chemistry laboratory parameters including absolute measurements and changes (absolute and percentage) from baseline by scheduled time points.

Abnormal laboratory results will be graded according to NCI-CTCAE version 5.0 as applicable. For some laboratory tests, the CTCAE criteria may include qualifying definitions (e.g., clinical AE and/or requirement for concomitant medication) in addition to the specific laboratory value used for the definition of the toxicity grades. For such tests, the qualifying definitions will not be used for the assignment of toxicity grades.

A shift table, presenting the 2-way frequency tabulation for baseline and the worst post-treatment value over the course of the trial according to the NCI-CTCAE grade will be provided for selected clinical laboratory tests including ALT, AST, total bilirubin, creatinine, amylase, lipase, GGT, GFR and hemoglobin. Both scheduled and unscheduled post-treatment visits will be considered in tabulation of the worst post-treatment value.

Additionally, the number and percentage of subjects with the following potentially clinically significant abnormal liver function test at post-baseline will be presented:

- ALT  $\geq 3 \times \text{ULN}$ ,  $\geq 5 \times \text{ULN}$ ,  $\geq 10 \times \text{ULN}$ , and  $\geq 20 \times \text{ULN}$

- AST  $\geq 3 \times \text{ULN}$ ,  $\geq 5 \times \text{ULN}$ ,  $\geq 10 \times \text{ULN}$ , and  $\geq 20 \times \text{ULN}$
- Total bilirubin  $\geq 2 \times \text{ULN}$
- Potential Hy's Law cases: ALT or AST  $> 3 \times \text{ULN}$ , total bilirubin  $\geq 2 \times \text{ULN}$ , and ALP  $< 2 \times \text{ULN}$  at the same visit

A listing of subjects with any Potential Hy's Law cases ordered chronologically will be presented. The listing will include the visits at which the Potential Hy's Law cases were met, with the value of the following collected parameters: ALT, AST, Total bilirubin, and ALP.

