##### 4.3.8.1 *Adverse events*

Adverse events (AEs) will be coded using Medical Dictionary for Regulatory Activities (MedDRA) version 24.0. The severity of all adverse events will be graded according to the National Cancer Institute (NCI) Common Terminology Criteria for Adverse Event (CTCAE) [NCI-CTCAE, 2017], version 5 (publication date: 27 November 2017). Adverse Events will be summarized descriptively by the frequency and incidence of subjects experiencing events corresponding to System Organ Class (SOC) MedDRA and Preferred Term (PT). Subjects with multiple occurrences of events will only be counted once at the maximum severity/grade to trial therapy for each PT, SOC, and overall. Summaries will be ordered by decreasing overall incidence in SOC; and by decreasing overall incidence of PTs within a SOC .

The overall observation period will be divided into mutually exclusive categories, including pre-treatment, on-treatment (treatment emergent), post-treatment:

- A treatment-emergent adverse event (TEAE) is defined as an adverse event with a start date and time on or after the first administration of apaglutide or having been present prior to the first dose of apaglutide but worsening in severity after starting treatment relative to the pre-treatment state. Adverse events are considered as TEAE until 28 days after the last dose of apaglutide received.
- A pre-treatment Adverse Event is defined as an AE occurring after the signature of the ICF and before the first dose.
- A post-treatment adverse event is defined as an AE occurring 28 days after the last dose.

Adverse events that are reported as possibly, probably, or definitely related to apaglutide therapy will be counted as related to trial therapy. Adverse events with a missing relationship will be considered as "related".

An overview of all Adverse Events will be provided.

All SAEs or AEs that led to withdrawal will be listed, Serious Adverse Events (SAEs) will be flagged within the listing.

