#### *4.3.8.1.3 Post-treatment Adverse Events Analysis*

The following type of events will be summarized by SOC and PT:

- 1) Adverse Events
- 2) Serious Adverse Events (SAE)
- 3) Grade 3-5 AE
- 4) Grade 5 AE
- 5) AE leading to study discontinuation
- 6) Related AE
- 7) Related Grade 3-5 AE
- 8) Related Grade 5 AE

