#### *4.3.8.2 Adverse events of Special Interest*

The overall frequency and incidence of subjects with treatment-emergent Adverse Events of special interest (AESI) (as collected in AE eCRF form) will be tabulated by PTs which were considered AESI overall and by apraglutide dose levels and overall:

- Injection site reactions
- Gastrointestinal obstructions
- Gallbladder, biliary and pancreatic disease
- Fluid overload
- Colorectal polyps
- Newly Diagnosed malignancies

- Systemic hypersensitivity

The following type of AESIs will be summarized by SOC and PT:

- 1) Adverse Events
- 2) Serious Adverse Events (SAE)
- 3) Grade 3-5 AE (CTCAE; version 5.0)
- 4) Grade 5 AE (CTCAE; version 5.0)
- 5) AE leading to study discontinuation
- 6) Related AE
- 7) Related Grade 3-5 AE (CTCAE; version 5.0)
- 8) Related Grade 5 AE (CTCAE; version 5.0)

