#### 4.3.8.3 Adverse events of Particular Interest

Treatment-emergent adverse events of particular interest (AEPI) are Sponsor defined and will be derived programmatically based on Sponsor-defined list of preferred terms (see Table 4-2), according to the Safety Signal Detection Plan (V1.0).

**Table 4-2: Sponsor-defined Adverse Events of Particular Interest. SMQ = Standardised MedDRA Queries, HLT= High Level Term.**

AEPI	Definition
Acceleration of neoplastic growth including Intestinal neoplastic growth/hypertrophic effect including polyps	SOC: Neoplasms benign, malignant and unspecified (including cysts and polyps)
Benign neoplasia of the Gastrointestinal tract including the hepatobiliary system (not including polyps).	SMQ: Gastrointestinal premalignant disorders (Level 1, narrow terms) SMQ: Biliary neoplasms benign (incl cysts and polyps) (Level 3, narrow terms)
Gastrointestinal obstruction	SMQ: Gastrointestinal obstruction (Level 2, narrow terms)
Gastrointestinal stoma obstruction	PT: Intestinal anastomosis complication, Stoma Obstruction

Increase of the liver transaminases	SMQ Drug related hepatic disorders - comprehensive search (broad and narrow terms)
Embryofetal toxicity	SMQ: Pregnancy and neonatal topics (broad and narrow terms)
Biliary adverse events	SMQ: Functional, inflammatory and gallstone related biliary disorders (broad and narrow terms)
Pancreatic adverse events	HLT: Acute and chronic pancreatitis HLT: pancreatitis disorders necrotizing entecorolitis (NEC)
Cardiovascular AEs associated with fluid overload	SMQ: Haemodynamic oedema, effusions and fluid overload (Narrow) SMQ. Cardiac failure (broad and narrow terms)
Cecal AE (additional from interim analysis)	LLT: Cecal diverticulitis, Cecal hemorrhage, Cecal infection, Cecal inflammation, Cecal lesion excision, Cecal obstruction, Cecum perforation, Cecal polyp, Cecal ulcer, Cecal volvulus, Cecum rupture

Treatment-emergent AEPIs will be summarized by SOC and PT and in total by apraglutide dose levels and in total for the following, where subjects with multiple adverse events will be counted only once per SOC or PT:

- 1) Treatment-emergent AEPIs
- 2) IMP-related TEAE
- 3) Grade 3-5 TEAE
- 4) Serious TEAEs
- 5) TEAEs leading to IMP dose reduction
- 6) TEAEs leading to IMP interruption
- 7) TEAEs leading to IMP permanently discontinued
- 8) AEs leading to death.

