#### *4.3.8.5 Vital Signs*

Descriptive statistics will be provided for systolic blood pressure, diastolic blood pressure, heart rate. Changes from baseline to scheduled visit and the minimum, maximum, and last post-baseline values will be presented. Both scheduled and unscheduled post-baseline values will be considered for summaries of the minimum, maximum, and last post-baseline values.

The number and proportion of subjects with potentially clinically significant changes in vital signs will be presented based on the following thresholds:

- Systolic blood pressure  $\geq 160 \text{ mmHg}$  and increase  $\geq 20 \text{ mmHg}$  from baseline
- Systolic blood pressure  $\leq 90 \text{ mmHg}$  and decrease  $\geq 20 \text{ mmHg}$  from baseline
- Diastolic blood pressure  $\geq 100 \text{ mmHg}$  and increase  $\geq 15 \text{ mmHg}$  from baseline
- Diastolic blood pressure  $\leq 50 \text{ mmHg}$  and decrease  $\geq 15 \text{ mmHg}$  from baseline
- Heart rate  $\geq 120 \text{ bpm}$  with increase  $\geq 15 \text{ bpm}$  from baseline
- Heart rate  $\leq 50 \text{ bpm}$  with decrease  $\geq 15 \text{ bpm}$  from baseline

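### Worst-value laboratory, liver, vital-sign and ECG summaries pool all time after first dose, while adverse events are cut at last dose + 28 days; adding the same cut is a cheap improvement, mainly for the EOT analysis

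*SAP*

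**What the plan says.** **Adverse events.** SAP 4.3.8.1 sets the time structure: "The overall observation period will be divided into mutually exclusive categories, including pre-treatment, on-treatment (treatment emergent), post-treatment". The boundary is explicit: "Adverse events are considered as TEAE until 28 days after the last dose of" the study drug. Sections 4.3.8.1.1 to 4.3.8.1.3 then give each period its own tables, the last headed "Post-treatment Adverse Events Analysis". Events of special interest (4.3.8.2) are restricted to treatment-emergent events, and so are those of particular interest (4.3.8.3): "Treatment-emergent AEPIs will be summarized by SOC and PT".

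**Other safety data.** Sections 4.3.8.4 to 4.3.8.6 set no upper date.

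- Laboratory shift table: "the worst post-treatment value over the course of the trial according to the NCI-CTCAE grade will be provided".
- Liver thresholds: the number of subjects with a "potentially clinically significant abnormal liver function test at post-baseline will be presented".
- Vital signs: "Both scheduled and unscheduled post-baseline values will be considered for summaries of the minimum, maximum, and last post-baseline values". The threshold counts that follow are also unbounded.
- ECG (4.3.8.6): a shift to the worst post-baseline result, and QTcF categories both by scheduled visit and at any time after baseline.

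Baseline is the last value before the first dose (SAP 4.1.1), so these outputs take every value from first dose to the data cut-off. SAP section 6, which lists changes from the protocol, does not mention the difference.

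**The concern.** Safety and tolerability are the primary objective, and every subject receives apraglutide. With no untreated arm, timing relative to dosing is one of the few pieces of attribution evidence available. Dosing lasts 8 or 13 weeks for most planned courses, within 104 weeks of follow-up. A worst grade taken over the whole trial can therefore come from long after exposure, in a population where the protocol itself expects abnormal liver tests (section 4.2.1.2).

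Two consequences follow. A worst liver grade or a threshold crossing cannot be placed on or off drug from the table alone. And a maximum post-baseline QTcF can read as on-drug evidence when, for the standard courses, its scheduled content is entirely off drug.

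**Working it through.** The plan states no figure on this point, so there is none to reproduce. The check is calendar arithmetic on protocol days (first dose = Day 0).

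**Inputs**

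- Courses (SAP 2.1): 8 doses (Weeks 0–7), 13 doses (Weeks 0–12), and up to 26 doses with optional treatment (to Week 25).
- Full local laboratory panels (SAP Tables B1 and B2, footnote 15): Days 7, 14, 21, 28, 42, 56, 91, 119, 147, 182, 364, 728, which is 12 in all. Dosing-only visits draw bilirubin alone.
- Post-baseline ECGs (same tables): Days 182, 364 and 728, plus the early-discontinuation visits. The SAP tables are used because the protocol's tables are not cleanly legible in the copy reviewed; SAP Appendix B says that the two correspond.

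**Window end** = last dose day + 28, with last dose day = 7 × (doses − 1).

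- 8 doses: 49 + 28 = Day 77
- 13 doses: 84 + 28 = Day 112
- 26 doses: 175 + 28 = Day 203

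**Scheduled assessments after the window, for completed courses without flare re-treatment**

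| | 8 doses | 13 doses | 26 doses |
|---|---|---|---|
| Full panels to Day 728 | 6/12 | 5/12 | 2/12 |
| Full panels to Day 182 | 4/10 | 3/10 | 0/10 |
| Full panels to Day 91 | 1/7 | 0/7 | 0/7 |
| Bilirubin to Day 728 | 6/14 | 5/18 | 2/28 |
| ECGs to Day 728 | 3/3 | 3/3 | 2/3 |
| ECGs to Day 182 | 1/1 | 1/1 | 0/1 |

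The bilirubin denominators add the dosing-only draws, all of which are inside the window: Weeks 5 and 7 (12 + 2 = 14); also Weeks 9–12 (14 + 4 = 18); also Weeks 14–16, 18–20 and 22–25 (18 + 10 = 28). No ECG is scheduled between baseline and Day 91, apart from any early-discontinuation visit.

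**ECG margins.** The Week 26 ECG falls 182 − 77 = 105 days after the window for 8 doses and 182 − 112 = 70 days after it for 13. One day of visit tolerance at each end leaves at least 68. That ECG is inside the window only if the last dose is on or after Day 182 − 28 = 154 (Week 22), which needs optional or flare treatment.

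**Early discontinuation.** The visit is 28 to 35 days after the last dose. After 4 doses (last dose Day 21, window to Day 49) it falls on Days 49–56. With follow-up to Week 104 there are 7 panels (Days 7, 14, 21, the visit, 182, 364, 728) and 4 ECGs. If the visit is on Day 49, 3/7 panels and 3/4 ECGs are after the window. If it is on Days 50–56, 4/7 and 4/4 are.

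**Flare re-treatment after 8 doses, dosed to Week 25.** One interval from first dose to Day 203 holds 10 of 12 panels. Restart at Week 17 (SAP Table B1, footnote 5) leaves a gap of Days 78–118, or 41 days, with one panel (Day 91). Restart at Week 18 (protocol Figure 3, footnote 3) leaves Days 78–125, or 48 days, with two panels (Days 91 and 119).

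These counts are of visits, not events. Unscheduled samples and vital signs are not counted, and subjects who die or withdraw contribute fewer late values.

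**The case against.** The strongest reply is that the on-drug signal already has dated routes.

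- Laboratory abnormalities judged clinically significant are recorded as adverse events (protocol 5.8.6 and 5.9.1), as are clinically significant ECG changes (5.8.5 and 7.6.6). These pass through the 28-day split.
- The events of particular interest include a treatment-emergent liver-transaminase category with broad and narrow terms (SAP 4.3.8.3).
- Dose modifications are summarised by reason (SAP 4.3.6.1), and safety-driven dose reductions must be documented as adverse events (protocol 6.6.2).
- By-visit summaries, including QTcF by visit, and the Hy's Law listing show timing.
- Protocol 7.6.3 asks for before-and-after shifts with no window, and a whole-trial worst value omits nothing.

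Most of this stands, and it is why the point is an improvement rather than a correction. Three gaps remain. Protocol 6.5 keeps abnormal findings out of adverse-event reporting unless they are symptomatic, lead to discontinuation or are judged clinically significant. Unscheduled values enter the worst-value derivations but otherwise appear only in listings (SAP 4.1.1), and the repeat liver tests required by protocol Table 6 may well be unscheduled. From Week 13, a calendar visit mixes subjects inside and outside the window: Day 91 is after it for 8 doses and within it for 13.

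It is also fair to say that splitting the table cannot repair the ECG schedule. The absence of scheduled on-drug ECGs is a data-collection matter.

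A reader might infer that every scheduled post-baseline ECG of any 8- or 13-dose subject is off drug. The documents do not support that. A subject who discontinues early may have an ECG exactly on the window edge, and one re-treated for flare to Week 22 or later has the Week 26 ECG inside it. Clinically indicated ECGs may also be done during treatment (protocol 5.8.5).

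**Conclusion.** The point holds as a cheap improvement worth considering. The plan uses two time conventions for its primary domain, and the worst, maximum and threshold summaries do not separate unscheduled values, or abnormalities that are not reported as adverse events, by period. For completed 8- and 13-dose courses without re-treatment, 6/12 and 5/12 scheduled full panels to Week 104, and all three follow-up ECGs, are outside the adverse-event window.

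The weight falls on the EOT analysis. To Day 91 only 1/7 or 0/7 panels are affected. The Primary Analysis takes all data to 01 Dec 2023, so earlier-enrolled subjects may add later values, but enrolment dates are not given and the extent is unknown. No laboratory or ECG event rates are given either, so the effect on any reported percentage cannot be sized.

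Two stronger readings should be set aside. One is that the laboratory shift table excludes on-drug values, because post-treatment has a narrower meaning in the adverse-event section. SAP 4.3.8.6 uses post-treatment and post-baseline for the same values, and protocol 7.6.3 wants shifts before and after therapy, so all values after first dose is the sensible reading. The other is that on-drug safety signals are missed. No recorded on-drug value is dropped, and clinically significant ones reach dated tables.

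The ECG conclusion rests on the schedule in SAP Tables B1 and B2.

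**What to change.** Add one sentence to each of SAP 4.3.8.4, 4.3.8.5 and 4.3.8.6. Present the worst-grade shift table, liver-threshold counts, vital-sign extremes and threshold counts, and ECG worst and any-time QTcF tables for first dose to last dose + 28 days, and separately for later values. Assign each value by its sample or assessment date, which also places the early-discontinuation visit. Show the number of subjects with at least one value in each period, and keep the whole-trial worst value as a supplement.

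For flare re-treatment, use the same interval as the adverse-event tables so that the outputs align, and flag values in the drug-free gap. In the 8-dose example above that means one or two flagged panels.

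As a clerical edit, replace post-treatment with post-baseline where it describes laboratory, ECG and physical-examination values (SAP 4.3.8.4, 4.3.8.6 and 4.3.8.7).

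No new data are needed and the date rule already exists. The cost is extra table columns, small on-treatment ECG counts, and a flag for flare subjects. Those small ECG counts are informative in themselves, because they tell the reader how few on-drug ECG values lie behind the summary.

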12. Clinically significant or uncontrolled cardiac disease including acute myocardial infarction within 6 months prior to randomization/Day 0, uncontrolled hypertension, congestive heart failure New York Heart Association Class III or IV
13. Requirement for vasopressor or inotropic support within 30 days prior to randomization/Day 0
14. Presence of uncontrolled cholestatic disorders or unresolved sinusoidal obstructive syndrome/veno-occlusive disease of the liver (defined as

⁴ Except methotrexate and mycophenolate mofetil

persistent bilirubin abnormalities not attributable to aGVHD and ongoing organ dysfunction)

15. Presence of relapsed primary malignancy or treatment for relapse after alloSCT
16. Requirement for unplanned immune suppression withdrawal as treatment of early malignancy relapse or low donor chimerism. Unclear remission states will be discussed with the Sponsor
17. Presence of newly diagnosed malignancies at screening or prior to randomization/Day 0
18. History of chronic gall bladder or bile duct inflammation or biliary obstruction unless a cholecystectomy was performed before screening
19. Presence or history of GI tumors (including the hepatobiliary system and pancreas) within the last five years before randomization; presence of colonic polyps that are not removed
20. Subjects that present or have a history of familial adenomatous polyposis
21. Presence of an active clinically uncontrolled infection or evidence of active tuberculosis (clinical diagnosis per local practice). Cytomegalovirus reactivation is permitted as long as no evidence of pulmonary disease is present.
22. Central venous catheter sepsis requiring systemic antibiotics within the previous 7 days prior to randomization/Day 0
23. Known cGVHD
24. Known active GI inflammation not related to GI-aGVHD (e.g., active inflammatory bowel disease such as Crohn's and ulcerative colitis)
25. History of progressive multifocal leuko-encephalopathy
26. Known pregnant or nursing (lactating) women
27. Known major abdominal surgery in the last 6 months prior to randomization/Day 0 (surgical feeding tube placement or other minimally invasive surgery is allowed)
28. History of clinically significant intestinal adhesions increasing the risk of GI obstruction or GI contrast examination findings suggesting subacute intestinal obstruction or stricture within 6 months prior to randomization/Day 0

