29. Liver enzymes meeting any of the following criteria within 48 hours prior to trial medication start:
 - a. Alanine aminotransferase (ALT) or aspartate aminotransferase (AST) $>8 \times$ upper limit of normal (ULN)
 - b. Alanine aminotransferase or AST $>5 \times$ ULN AND international normalized ratio >3

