4.2.1.2 Apraglutide Dose Adjustments, Interruptions and Stopping Rules

For subjects who do not tolerate the protocol dosing schedule, dose adjustments, or interruptions are mandated to allow the subjects to continue the trial medication and maintain apraglutide dosing for optimal treatment of aGVHD. The objective of these dose adjustment rules is to optimize response for each individual subject while avoiding clinically relevant toxicities attributed to apraglutide.

Dose reductions should be undertaken as outlined in Table 5.

Table 5: Dose Reduction Steps for Apraglutide

Original dose (mg)	2.5	4	5	7.5	10
New dose (mg)	0	2.5	4	5	7.5

Deviations to the recommended dose reductions, temporary interruptions, or permanent interruptions will need to be documented.

Subjects who are receiving multiple oncological treatments, or are dependent on parenteral support, develop abnormal liver function tests. In both cases bilirubin, ALT,

and/or AST may be elevated at baseline; therefore, the stopping rules for these subjects will use the increase from baseline instead of values from the ULN.

Table 6 depicts the dose adjustments for apaglutide dose in case of deviations of clinical safety parameters starting from Week 1.

Table 6: Apaglutide Dose Adjustments—Holding and Stopping Rules

Total bilirubin elevated (adapted from MAGIC)	
Use x ULN if normal at baseline (BSL) or x BSL if elevated at BSL	
>1.5–3.0 x ULN or BSL	Recommendation: Maintain dose level
>3.0–5.0 x ULN or BSL	
Mandatory: reduce by 1 dose level
 
Monitor LFTs weekly, or more frequently if clinically indicated, until resolved to $\leq 3.0 \times$ ULN/BSL:
 
 • If resolved in ≤ 14 days, then return to initial dose level • If resolved in >14 days, then maintain the dose level minus 1
>5.0–10.0 x ULN or BSL	
Mandatory: Hold dosing
 
Monitor LFTs weekly, or more frequently if clinically indicated, until resolved to $\leq 3.0 \times$ ULN/BSL:
 
 • If resolved in ≤ 14 days, then resume at initial dose level • If resolved in >14 days, then resume at dose level minus 1

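### The SAP's post-baseline liver threshold counts and potential Hy's law cases ignore baseline, so subjects who entered with raised values can be counted without any worsening

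*SAP*

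**What the plan says.** SAP 4.3.8.4 announces that "the number and percentage of subjects with the following potentially clinically significant abnormal liver function test at post-baseline will be presented". The rows are ALT and AST at or above 3, 5, 10 and 20 × ULN and total bilirubin at or above 2 × ULN. The last row begins "Potential Hy's Law cases: ALT or AST" and requires ALT or AST above 3 × ULN, bilirubin at or above 2 × ULN and ALP below 2 × ULN, all at one visit. None of these rows refers to the subject's baseline. Of the accompanying listing the SAP says: "The listing will include the visits at which the Potential Hy's Law cases were met", with ALT, AST, bilirubin and ALP. Baseline values are not mentioned.

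On entry, Protocol 3.2.2, exclusion 29, is headed "Liver enzymes meeting any of the following criteria within 48 hours prior to trial medication start". It excludes ALT or AST above 8 × ULN, or above 5 × ULN together with INR above 3. Exclusion 14 covers hepatic conditions defined by "persistent bilirubin abnormalities not attributable to aGVHD and ongoing organ dysfunction". Bilirubin raised by acute GVHD is therefore not excluded, and no numeric bilirubin ceiling is set.

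Protocol 4.2.1.2 acknowledges that bilirubin, ALT and AST may be raised at baseline, so that "the stopping rules for these subjects will use the increase from baseline instead of values from the ULN". Table 6, including its combined ALT/AST and bilirubin rule, uses ULN if baseline is normal and baseline (BSL) if it is elevated. The laboratory safety endpoint in Protocol 1.5.2.1 and SAP 3.1 is expressed as clinically significant change from baseline, liver tests included.

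**The concern.** A count of post-baseline values over a fixed ULN multiple measures new liver injury only if subjects start below that multiple. Here the entry criteria allow them to start above it. The rows then mix pre-existing disease with new elevation, and they cannot separate worsening from improvement: ALT moving from 6 to 9.9 × ULN and ALT moving from 6 to 5.5 × ULN fall in exactly the same rows.

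Safety is the primary objective, and a potential Hy's law count draws more attention than most laboratory tables. Both randomized arms receive apraglutide, and SAP Section 6 (item 7) drops the external comparison for the Primary Analysis. With no untreated arm, each subject's own baseline is the main reference for what is new. Protocol 6.6.3 also takes its liver toxicity events from Section 4.2.1.2, which uses the ULN/BSL convention. The same subject could thus be a potential Hy's law case in the report without meeting the combined rule used in monitoring.

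**Working it through.** The plan states no figure to reproduce. The check applies the SAP rule and the protocol's combined rule to constructed subjects who satisfy the enzyme and bilirubin entry criteria.

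**Rules**
- SAP potential Hy's law: ALT or AST > 3 × ULN, bilirubin ≥ 2 × ULN, ALP < 2 × ULN, same visit.
- Protocol Table 6 combined rule: ALT/AST > 3 × reference and bilirubin > 2 × reference, where the reference is ULN if baseline is normal and the baseline value if it is elevated.

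**Constructed subjects** (multiples of ULN, ALT/bilirubin; ALP set at 1.5 × ULN by assumption; entry above 5 × ULN requires INR not above 3)

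| Baseline | Post-baseline | SAP rows met | SAP Hy's law | Protocol combined rule |
|---|---|---|---|---|
| 7.9 / 1 | 7.9 / 1 | ALT ≥3, ≥5 | no | no |
| 6 / 1 | 3.5 / 1 | ALT ≥3 | no | no |
| 4 / 2.8 | 4 / 2.8 | ALT ≥3, bilirubin ≥2 | yes | no (ratios 1.0 and 1.0) |
| 6 / 5 | 3.2 / 2.1 | ALT ≥3, bilirubin ≥2 | yes | no (3.2/6 = 0.53; 2.1/5 = 0.42) |
| 1 / 1 | 3.5 / 2.2 | ALT ≥3, bilirubin ≥2 | yes | yes |
| 4 / 2.8 | 12.5 / 5.7 | ALT ≥3, ≥5, ≥10, bilirubin ≥2 | yes | yes (12.5/4 = 3.13; 5.7/2.8 = 2.04) |

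The first four subjects are stable or improving and are all counted somewhere; two of them are potential Hy's law cases. The last two have worsened and meet both rules. With ALP at or above 2 × ULN, none of the six would be a Hy's law case under the SAP.

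**Can liver GVHD alone satisfy the bilirubin condition?** Protocol Appendix 16.3 sets liver Stage 1 at 2–3 mg/dL and Stage 2 from 3.1 mg/dL. The documents give no bilirubin ULN; 1.0–1.5 mg/dL is assumed.
- Stage 1: from 2/1.5 = 1.3 to 3/1.0 = 3.0 × ULN, so only some subjects reach 2 × ULN.
- Stage 2, lower limit: from 3.1/1.5 = 2.1 to 3.1/1.0 = 3.1 × ULN, so all do.

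**Weight of one subject:** 1/15 = 6.7 percentage points in an arm; 1/30 = 3.3 among all randomized.

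**How many might be affected?** Baseline prevalence is not in the documents. The table assumes a proportion p of the 30 randomized subjects enter at or above a given threshold.

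| p | Expected, 30p | Chance of at least one, 1 − (1 − p)^30 |
|---|---|---|
| 5% | 1.5 | 79% |
| 10% | 3 | 96% |
| 20% | 6 | >99% |
| 30% | 9 | >99% |

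These are upper limits on the miscount: a subject is counted only if a post-baseline value is still over the threshold.

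**The case against.** The strongest reply is that baseline is handled elsewhere. SAP 4.3.8.4 itself gives absolute and percentage changes from baseline, and a baseline-to-worst CTCAE shift table for ALT, AST and total bilirubin. Treatment-emergent events must be new or worsened (SAP 4.3.8.1), and the liver transaminase event of particular interest is restricted to treatment-emergent events (4.3.8.3). Liver stage is tabulated at baseline and by visit (4.3.3, 4.3.9.1), and Protocol 7.6.3 says laboratory results will be listed. This stands for single analytes: a reader can partly separate old from new. It does not reach the combined criterion, because separate shift tables cannot show whether ALT or AST, bilirubin and ALP met it together at baseline.

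A second reply is that Table 6 governs dosing of individual subjects, not reporting, so the SAP breaches nothing. That also stands; the finding is a mismatch of convention and of fit to the endpoint. The SAP's practice elsewhere is mixed. For vital signs it says "The number and proportion of subjects with potentially clinically significant changes in vital signs will be presented based on the following thresholds", and each threshold is paired with a change from baseline; for QTcF it puts absolute cut-offs and increases in separate rows.

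Third, a ULN screen is deliberately sensitive and reasonable with at most 34 subjects. Removing everyone who met the criteria at baseline would lose real injury: a subject going from ALT 3.2 and bilirubin 2.1 to 15 and 8 × ULN would leave the count. This is right, and it shapes the fix.

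**Conclusion.** The point holds, limited to the threshold counts, the potential Hy's law count and its listing. As written, they can include subjects with no worsening, and no output separates pre-existing from new combined cases. This rests on the text of the SAP and the entry criteria. The Hy's law part also needs ALP below 2 × ULN, and the documents do not say how often that holds in subjects with liver GVHD.

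Three stronger readings are tempting and are not supported.
- A reader might infer that the SAP reports baseline disease as a drug effect. It calls the cases potential and the values post-baseline; attribution would be the reader's step.
- A reader might infer that the whole laboratory analysis ignores baseline. The shift tables and change summaries show otherwise.
- A reader might put a size on the distortion or predict a false dose effect. Without baseline prevalence no size can be derived. SAP Section 6 (item 12) rules out a formal dose comparison, although arms of 15 shown side by side do leave room for chance imbalance at 6.7 points per subject.

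The defect is worth correcting because liver tests belong to the primary safety assessment and there is no untreated arm to compare with.

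**What to change.** Amend SAP 4.3.8.4 as follows.
- Keep the ULN-based table as a sensitive screen.
- Present each row, and the potential Hy's law count, by baseline status.
- Among subjects below the threshold at baseline, report new crossings, with those subjects as the denominator.
- Among subjects at or above it at baseline, report the worst post-baseline value as a multiple of baseline.
- Keep every potential Hy's law case in the listing, flag those already meeting the criteria at baseline, and add baseline ALT, AST, bilirubin and ALP so that worsening remains visible.
- State in the SAP how these displays relate to the protocol's ULN/BSL convention.

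The cost is a few extra table rows, four listing columns and a flag, and minor programming. Baseline local laboratory tests, ALP included, are already collected. The price in reporting is smaller denominators in the split rows, which is why the unsplit table should stay beside them.
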